6.8.2. Laboratory Data

Laboratory data will be listed and summarized in accordance with the CaPS reporting standards. Summaries of subjects meeting pre-specified discontinuation criteria will be created using methods for categorical data.

6.8.3. Vital Signs

Vital signs will be summarized at all visits per SoA.

6.8.4. Electrocardiograms

ECG parameters, if applicable, will be summarized at baseline, Week 4, Week 16/End of Treatment visits and at Week 40.

6.8.5. Physical Examination

Physical examinations will be summarized at all-available post-baseline visits.

7. INTERIM ANALYSES

7.1. Introduction

There will be an interim analyses for this study. *Interim analyses will be performed to assess efficacy and safety after at least 60% of the planned participants, ie, approximately 80 participants, complete their study participation through Week 12. Interim analysis results will be used for internal business decisions regarding future study planning or stopping for futility. Before the interim analysis is instigated, the details of the objectives, decision criteria, dissemination plan and method of maintaining the study blind as per Pfizer's SOPs will be documented and approved in the internal review committee (IRC) charter.*

7.2. Interim Analyses and Summaries

A separate interim analysis plan may be developed, if needed.

Appendix 1. Summary of Efficacy Analyses

Endpoint	Analysis Type	Population	Data Inclusion and Rules for Handling Intercurrent Events and Missing Data	Analysis Model
Proportion of achieving PASI90 at Week 16	Main Analysis	FAS	Prohibited medication/withdrawal and all other missing data will be treated as treatment failure	Chan and Zhang
Binary endpoints for PASI 75, PASI 90, PGA (0/1 and ≥ 2), PGA (0/1) at all time points	Sensitivity/Supplementary Analysis	FAS	Observed data	GLMM
Binary endpoints for PASI 75, PASI 90, PGA (0/1 and ≥ 2), PGA (0/1), CCI [REDACTED] PSI (≤ 8 and 0/1), CCI [REDACTED]	Main Analysis	FAS	Prohibited medication/withdrawal and all other missing data will be treated as treatment failure	Chan and Zhang
Continuous endpoints for PASI	Main Analysis	FAS	Multiple Imputation	ANCOVA
Continuous endpoints for PASI, CCI [REDACTED] PP-NRS, PSI, CCI [REDACTED]	Sensitivity/Supplementary Analysis	FAS	Observed data	MMRM

Appendix 2. Data Derivation Details

Appendix 2.1. Definition and Use of Visit Windows in Reporting

Visit windows will be used for efficacy variables, and for any safety data that display or summarize by study visit.

Visit No.	Visit Label	Target Day	Visit Window ^d
1	Screening	N/A	$-42 \leq \text{day} \leq -1$
2	Baseline ^a	1	day = 1
3	Week 1	8	$2 \leq \text{day} \leq 11$
4	Week 2	15	$12 \leq \text{day} \leq 21$
5	Week 4	29	$22 \leq \text{day} \leq 35$
6	Week 6	43	$36 \leq \text{day} \leq 49$
7	Week 8	57	$50 \leq \text{day} \leq 70$
8	Week 12	85	$71 \leq \text{day} \leq 98$
9	Week 16 ^b	118	$99 \leq \text{day} \leq \text{MIN} (129, \text{first dosing day at Week 18} - 1)$
10	Week 18 ^b	127	$\text{MIN} (129, \text{first dosing day at Week 18} - 1) + 1 \leq \text{day} \leq 133$
11	Week 20	141	$134 \leq \text{day} \leq 154$
12	Week 24	169	$155 \leq \text{day} \leq 182$
13	Week 28	197	$183 \leq \text{day} \leq 210$
14	Week 32	225	$211 \leq \text{day} \leq 238$
15	Week 36	253	$239 \leq \text{day} \leq 266$
16	Week 40 ^c	281	$267 \leq \text{day} \leq 305$

a. Baseline analysis visit window may be considered as day ≤ 1 in some analyses (eg, those involving change from baseline). That is, in case that Day 1 observation is missing, the last observation by the first dosing date may be considered as the baseline. The baseline measurements for demography, height, pre-study medical history and medications will be collected at the “Screening” visit.
 
b. If the nominal week 16 assessments happened at the same day as Week 18 dosing, for all the efficacy and safety endpoints analyses by visit, that day will be counted as Week 16 visit, but for the dosing and compliance analysis, that day will be counted as Week 18 visit.
 
c. For the last on treatment visit of Week 40, we extended the visit window to include more data collected in the study. And here day 305 is the day before the scheduled target day of follow-up visit (309\pm3).
 
d. For multiple observations fall into a same window, following algorithm will be taken to identify the observation for analysis:
 
 1. The observation closest to the targeted day will be used. 2. If the observations are with equal distant from the targeted day in absolute value, the one after the targeted day will be used. 
All observations will, however, be included in the listings.
			

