6.1. Study Intervention(s) Administered

Blinded PF-06826647 and matching placebo will be provided as tablets for oral administration. PF-06826647 will be provided in dosage strengths of 100 mg and 25 mg tablets. PF-06826647 and matching placebo will be supplied in blister cards and labeled according to local regulatory requirements.

Intervention Name	PF-06826647	PF-06826647	PF-06826647	PF-06826647	Placebo
ARM Name	PF-06826647 50 mg	PF-06826647 100 mg	PF-06826647 200 mg	PF-06826647 400 mg	Placebo
Type	Drug	Drug	Drug	Drug	Drug
Dose Formulation	Tablet	Tablet	Tablet	Tablet	Tablet
Dosage Level(s)	50 mg QD	100 mg QD	200 mg QD	400 mg QD	Placebo
Number and Type of Tablets During Investigational Treatment Period, Day 0 to Week 16 (Number of Tablets)	2 x 25 mg active, and 4 x 100 mg size placebo	2 x 25 mg size placebo, and 1 x 100 mg active, and 3 x 100 mg size placebo	2 x 25 mg size placebo, and 2 x 100 mg active, and 2 x 100 mg size placebo	2 x 25 mg size placebo, and 4 x 100 mg active	2 x 25 mg size placebo, and 4 x 100 mg size placebo
Number and Type of Tablets During Extension Treatment Period, Week 16 to Week 40 (Number of Tablets)	2 x 100 mg active, and 2 x 100 mg size placebo or 4 x 100 mg active	2 x 100 mg active, and 2 x 100 mg size placebo or 4 x 100 mg active	2 x 100 mg active, and 2 x 100 mg size placebo	4 x 100 mg active	2 x 100 mg active, and 2 x 100 mg size placebo or 4 x 100 mg active
Route of Administration	Oral	Oral	Oral	Oral	Oral
Investigational Medicinal Product (IMP) and Noninvestigational Medicinal Product (NIMP)	IMP	IMP	IMP	IMP	N/A
Sourcing	Provided centrally by the sponsor IP should be provided as outlined in the Investigational Product Manual.	Provided centrally by the sponsor IP should be provided as outlined in the Investigational Product Manual.	Provided centrally by the sponsor IP should be provided as outlined in the Investigational Product Manual.	Provided centrally by the sponsor IP should be provided as outlined in the Investigational Product Manual.	Provided centrally by the sponsor IP should be provided as outlined in the Investigational Product Manual.

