Packaging and Labeling	Study intervention will be provided as tablets in blinded blister cards. Each blister card will be labeled as required per country requirement.	Study intervention will be provided as tablets in blinded blister cards. Each blister card will be labeled as required per country requirement.	Study intervention will be provided as tablets in blinded blister cards. Each blister card will be labeled as required per country requirement.	Study intervention will be provided as tablets in blinded blister cards. Each blister card will be labeled as required per country requirement.	Study intervention will be provided as tablets in blinded blister cards. Each blister card will be labeled as required per country requirement.

Participants will receive blinded labeled supplies throughout the study. To accomplish this, all participants will take a total of six tablets per day during the Investigational Treatment Period, and four tablets per day during the Extension Treatment Period.

The participants continuing into the Extension Treatment Period that were originally randomized to the 200 mg and 400 mg treatment groups in the Investigational Treatment Period will continue on their respective doses, while those randomized to one of the other treatment groups including placebo will be randomly assigned at study baseline to either receive 200 mg or 400 mg during the Extension Treatment Period.

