6.1.1. Administration

Participants will swallow the investigational product (IP) whole and will not manipulate or chew the IP prior to swallowing. Participants will administer IP as outpatients, except on study visit days. On study visit days, participants should not take their dose of study drug until instructed to do so by the investigator or designated study site staff while at the study site.

Blinded PF-06826647 tablets and matching placebo for oral administration will be dispensed in blisters. Participants will be provided dosing instructions.

Sites will be trained on how participants should take tablets at home through an Investigational Product manual and/or other vehicle(s). Sites are responsible for communicating this information to participants; and site staff should review the dosing instructions with participants at every study visit.

Participants should take the IP orally once daily during the Investigational Treatment Period and the Extension Treatment Period of the study.

A temporary hold on dosing of the investigational product during the study for an individual participant for up to a maximum of 7 consecutive days is allowed once from Day 1 to Day 113, if the principal investigator (PI) deems it necessary because of infections (eg, upper respiratory infection, urinary tract infection), gastrointestinal (GI) disorders (eg, diarrhea, nausea, vomiting) or hematological abnormalities. Any temporary hold on dosing of the investigational product during the study should be recorded in the case report form (CRF).

It is recommended that the tablets be swallowed whole with ambient temperature water to a total volume of approximately 240 mL, and not to manipulate or chew the medication prior to swallowing; and **it is recommended to be taken with food**. On study visit days, participants are to be instructed to refrain from dosing at home and are to take the dose in the clinic from their current blister card and the dose from the newly dispensed blister card will be taken on the next day at home.

If a dose is missed and the interval to the next dose is less than 8 hours, the missed dose should not be administered.

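### The SAP's Week 16 window targets Day 118 where the protocol has Day 113, and its upper bound rests on an undefined dosing day; either can change primary PASI 90 status, probably for few participants.

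*SAP*

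**What the plan says.** SAP Appendix 2.1 applies visit windows to the efficacy variables, and so to the primary endpoint, PASI 90 at Week 16.

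- **Target.** The Week 16 row has target Day 118. Protocol 1.3 (Schedule of Activities) places Week 16 on Study Day 113 with a window of ±2 days.
- **Window.** It runs from Day 99 to MIN(129, D − 1), where D is the "first dosing day at Week 18". The Week 18 window starts the day after that bound and ends on Day 133. D is not defined, and no value is given for a participant who has no such dose.
- **Choice of record.** Footnote d states: "The observation closest to the targeted day will be used". For records equally distant from the target, "the one after the targeted day will be used".
- **Same-day rule.** Footnote b begins "If the nominal week 16 assessments happened at the same day as Week 18 dosing". It counts that day as Week 16 for visit-based efficacy and safety analyses, but as Week 18 for dosing and compliance.
- **Treatment change.** The Protocol 6.1 table has the row "Number and Type of Tablets During Extension Treatment Period, Week 16 to Week 40". Participants not on 200 mg or 400 mg, "including placebo will be randomly assigned at study baseline to either receive 200 mg or 400 mg during the Extension Treatment Period". Under Protocol 6.1.1, after a clinic visit "the dose from the newly dispensed blister card will be taken on the next day at home".
- **No usable record.** For the primary estimand's data set, SAP 4.4 codes missing data as failure, and likewise data after withdrawal of study drug.

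**The concern.** Week 16 is the last placebo-controlled assessment and carries the primary comparison. From then on, placebo, 50 mg and 100 mg participants receive 200 mg or 400 mg. The rule that fixes which PASI record counts as Week 16 should therefore follow the protocol schedule and leave no room for interpretation.

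Two separate defects stand in that row. The target day governs the choice among several records in the window. The upper bound governs whether a record is in the window at all. The first can matter only for participants with more than one record in the window; the second can also matter for a participant with a single record.

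**Working it through.** **1. Which target fits the table?** The rule 7 × week + 1 gives 8, 15, 29, 43, 57, 85, 113, 127, 141, 169, 197, 225, 253 and 281 for the 14 post-baseline visits. The SAP matches 13 of them. Week 16 is the exception: 7 × 16 + 1 = 113, against 118, a difference of 5 days.

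The lower bounds give a second check. Leaving aside the Week 16/18 boundary, which is a formula, there are 12 fixed boundaries between rows. Each should be the midpoint of adjacent targets, rounded up.
- With Week 16 at 113: (85 + 113)/2 = 99, as printed; 12 of 12 boundaries fit.
- With Week 16 at 118: (85 + 118)/2 = 101.5, so 102, not 99; 11 of 12 fit.

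No footnote explains Day 118, although footnote c does explain the widened Week 40 window.

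**2. Effect of the target.** With one record in the window, the target plays no part. With two, take an on-time record on Day 113.
- Target 118: Day 113 is 5 days away. Days 114-122 are at most 4 days away and win; Day 123 ties at 5 and wins as the later record. So Days 114-123 displace it.
- Target 113: Day 113 is 0 days away, so nothing displaces it.

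This requires a window that reaches the second record, which depends on D.

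**3. Two readings of D.**
- *First Extension-period dose.* If the new card starts the day after the Week 16 visit (Protocol 6.1.1), then D − 1 is the Week 16 visit day. For on-schedule participants the window ends on Days 111-115, and Day 118 lies outside its own window.
- *Week 18 clinic dose.* With Week 18 at Day 127 ± 3 (Days 124-130), the window ends on Days 123-129.

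Footnote b fits the first reading better. On the second, a nominal Week 16 assessment on the dosing day would fall on Day 124 at the earliest, 124 − 115 = 9 days after the latest permitted Week 16 day.

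**4. Effect of the bound on a single record.** Suppose the first Extension dose is on Day 114, the only PASI is on Day 116, and the Week 18 clinic dose is on Day 127.
- First Extension dose: the bound is 114 − 1 = 113. Day 116 belongs to Week 18, so Week 16 is missing and coded as failure.
- Clinic dose: the bound is 127 − 1 = 126. Day 116 is the Week 16 record.

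Footnote b does not settle this, because it covers only assessment and dosing on the same day.

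**5. Scheduled visits.** Pair Week 16 on Days 111-115 with Week 18 on Days 124-130: 5 × 7 = 35 pairs.
- Under either reading of D, with the dose recorded, the Week 18 record lies outside the Week 16 window: 0 of 35 switch with either target.
- If the Day 129 cap applies, for instance because D means the clinic dose and none was taken, 3 of 35 switch with target 118: (111, 124) with distances 7 and 6; (111, 125), tied at 7; (112, 124), tied at 6. With target 113, none do.

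**6. Size per participant.** 1/40 = 2.5 percentage points in the placebo, 200 mg and 400 mg arms; 1/20 = 5 points in the 50 mg and 100 mg arms. The documents do not allow the number of affected participants to be computed.

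**The case against.** The strongest reply is that little follows in practice. Footnote b points to the first Extension dose. On that reading the window closes before the switch, and Day 118 simply selects the latest pre-switch record, normally the nominal visit. The second records needed are also uncommon. Protocol 1.3 allows unplanned visits to protect participants' well-being and schedules no PASI at them. Early Termination visits are for those who stop before Week 16 or leave the Extension early; someone who completes Week 16 and does not continue has a Week 20 Follow-Up visit instead. All of this stands, and it is why the point is minor. It does not justify Day 118, and it does not supply the missing definition.

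A second objection also stands: Day 113 alone can do worse. A nominal visit on Day 115, inside the ±2 window, is 2 days from 113 and loses to an unplanned PASI on Days 112-114. A late pre-switch visit on Day 120 is 7 days away and loses to one on Days 107-119; with target 118 it loses only to Days 117-119. The change of target therefore needs a precedence rule beside it.

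Protocol 6.1.1 permits one temporary dosing hold, which "is allowed once from Day 1 to Day 113". That agrees with the schedule but restates it, so it is not independent evidence for an analysis target.

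A reader might infer that Day 118 systematically draws post-switch data into the placebo comparison. The documents do not support this: the better reading of the bound excludes such records, and a single on-schedule record is the Week 16 record under either reading.

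**Conclusion.** Day 118 is a wrong figure in an operative rule, and the upper bound is undefined. Both bear on the primary endpoint. The severity is minor.

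The target error acts only through a second record in the window. The bound can also decide the status of a participant with a single record. The direction is not fixed. A PASI taken after the switch would tend to raise response in the placebo, 50 mg and 100 mg arms, whereas an Early Termination record set to failure, or a sole late record assigned to Week 18, would lower it. Few participants are likely to be affected; the day ranges above count calendar days, not participants or probabilities.

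The mismatch in the target rests on no assumption. The worked cases assume that the new card starts the day after the Week 16 visit and, where stated, that the Day 129 cap applies when no bounding dose exists. The failure coding of a sole late record leaves aside the separate COVID-19 rules in SAP 4.5.

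**What to change.** In SAP Appendix 2.1:

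1. Set the Week 16 target to Day 113, to match the Schedule of Activities.
2. Give the nominal Week 16 visit precedence over unplanned and Early Termination records in the window. This removes the losses that Day 113 alone would create.
3. Define the bounding date as the first Extension-period dose, in the Week 16 row, the Week 18 row and footnote b. Keep footnote b's same-day allowance.
4. State that the Day 129 cap applies to participants with no Extension dose.
5. State that, footnote b's same-day case apart, no assessment after the first Extension dose is used for Week 16.

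The cost is a table and footnote edit and a small programming change. There is one analytic cost: a participant whose only Week 16 PASI falls after the first Extension dose is counted as a failure. The SAP should say so, and the report should give the number of such participants.

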1.2. Schema

1.3. Schedule of Activities (SoA)

The SoA table provides an overview of the protocol visits and procedures. Refer to the [STUDY ASSESSMENTS AND PROCEDURES](#) section of the protocol for detailed information on each procedure and assessment required for compliance with the protocol.

The investigator may schedule visits (unplanned visits) in addition to those listed in the SoA table, in order to conduct evaluations or assessments required to protect the well-being of the participant

Study Procedure	Screening	Baseline	Investigational Treatment Period							Extension Treatment Period		Follow-Up ^b	Early Termination ^c
			1	2	4	6	8	12	16	18/20/24/28/32/36	40		
Visit Identifier (Week)	-6 to -1	0	1	2	4	6	8	12	16	18/20/24/28/32/36	40	20 or 44	
Study Day ^a	-42 to -1	1	8	15	29	43	57	85	113	127/141/169/197/225/253	281	141 or 309	
Visit Window (Days)	N/A		±1	±1	±2	±2	±2	±2	±2	±3	±3	±3	
Enrollment Procedures													
Informed consent	X												
Medical history & demography	X												
Eligibility assessment	X	X											
Medication History	X												
Randomization		X											
Clinical Assessments													
Full Physical Exam	X	X							X		X		X
Brief Physical Exam			X	X	X	X	X	X		X		X	
Vital signs ^d	X	X	X	X	X	X	X	X	X	X	X	X	X
ECG ^d	X	X			X				X		X		X
Height/Weight ^e	X	X							X		X		
Chest radiograph ^f	X												
C-SSRS ^g	X	X							X		X		
Laboratory Assessments													
Hematology/Blood chemistry	X	X	X	X	X	X	X	X	X	X	X	X	X
Lipid panel ^h (fasting)		X			X				X		X		
Urinalysis ⁱ	X	X			X				X		X		
FSH ^j	X												
Serum β-HCG ^k	X												

Study Procedure	Screening	Baseline	Investigational Treatment Period							Extension Treatment Period		Follow-Up ^b	Early Termination ^c
			1	2	4	6	8	12	16	18/20/24/28/32/36	40		
Visit Identifier (Week)	-6 to -1	0	1	2	4	6	8	12	16	18/20/24/28/32/36	40	20 or 44	
Study Day ^a	-42 to -1	1	8	15	29	43	57	85	113	127/141/169/197/225/253	281	141 or 309	
Visit Window (Days)	N/A		±1	±1	±2	±2	±2	±2	±2	±3	±3	±3	
Urine β-HCG ^l (done at site)		X	X	X	X	X	X	X	X	X	X	X	X
HIV serology/HBsAg, HBcAb, (HepB reflex testing), and HCVAb ^m	X												
Tuberculosis test ⁿ	X												
CCI [REDACTED]													
CCI [REDACTED]													
Study treatment													
IP dispensing ^q		X	X	X	X	X	X	X	X	X	X		
IP accountability			X	X	X	X	X	X	X	X	X	X	X
Dosing diary ^r			X	X	X	X	X	X	X	X	X	X	X
Clinical Assessments of psoriasis													
PASI, CCI PGA	X	X	X	X	X	X	X	X	X	X	X	X	X
PROs ^s													

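### SAP Appendix 2.1 prints the Week 16 target as Day 118 instead of Day 113, and that number decides which of two records counts as Week 16

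*SAP*

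**What the plan says.** SAP Appendix 2.1 opens by setting the scope: "Visit windows will be used for efficacy variables, and for any safety data that display or summarize by study visit". The table therefore governs the primary endpoint as well as by-visit safety summaries.

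The Week 16 row gives target Day 118. Its window runs from Day 99 to the earlier of Day 129 and the day before the first Week 18 dose.

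Footnote d settles the case of several records in one window. The first rule is "The observation closest to the targeted day will be used". The second is a tie-break: "If the observations are with equal distant from the targeted day in absolute value, the one after the targeted day will be used". Both rules use the printed target.

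Protocol 1.3 (Schedule of Activities) puts Week 16 at study Day 113 with a window of ±2 days. Protocol 6.1.1 uses the same day as the end of the 16-week period: a temporary dosing hold "is allowed once from Day 1 to Day 113".

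SAP 4.4 defines the data sets that use the selected record:
- **Primary categorical set:** data after withdrawal of study drug are set to failure.
- **Continuous (E2) set:** only data after prohibited medication are set to missing.
- **Observed set:** nothing is altered.

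**The concern.** The two documents give different days for the primary time point, and the SAP's day is the one the selection rule uses. Day 118 lies outside the protocol's own visit window of Days 111 to 115, so a visit held exactly on schedule is treated as five days early. Any later record in the window can then displace it.

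A later record is likely to be worse evidence about Week 16. It may come from an Early Termination or follow-up visit made after the drug was stopped. At stake is whether a participant's Week 16 status comes from the planned on-treatment assessment or from an off-drug one.

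**Working it through.** **1. Is 118 consistent with the rest of the table?** The rule is target = 7 × week + 1.
- Weeks 1, 2, 4, 6, 8 and 12 give 8, 15, 29, 43, 57 and 85. All match the printed targets.
- Weeks 18, 20, 24, 28, 32, 36 and 40 give 127, 141, 169, 197, 225, 253 and 281. All match.
- Week 16 gives 7 × 16 + 1 = 113. The table prints 118, a difference of 5.

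So 13 of 14 agree with the rule and with the Schedule of Activities. Nor is 118 the middle of the window, which is (99 + 129)/2 = 114.

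**2. What the target does.** Take a visit on day v, a later record on day r in the same window, and target T. The later record is chosen when |r − T| ≤ |v − T|, because ties go to the later one. If v < T, that means r ≤ 2T − v. If v ≥ T, the visit is never displaced.

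| Week 16 visit day | Last day that displaces it, T = 118 | Last day that displaces it, T = 113 |
|---|---|---|
| 111 | 125 | 115 |
| 112 | 124 | 114 |
| 113 | 123 | none |
| 114 | 122 | none |
| 115 | 121 | none |

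**3. Who has two records in the window?**
- *Participants entering the Extension.* Protocol 6.1.1 says "the dose from the newly dispensed blister card will be taken on the next day at home", and footnote b covers the case "If the nominal week 16 assessments happened at the same day as Week 18 dosing". Together these suggest that the Week 16 window closes when Extension dosing starts, normally the day after the visit. Nothing later is then left in it.
- *Participants who complete Week 16 and do not continue.* Their Follow-Up is at Week 20, Day 141 ± 3, which is outside the window.
- *Participants stopped at the Week 16 visit.* Protocol 7.1 asks for an Early Termination visit one week after the last dose. The Schedule of Activities lists PASI and PGA there.
- *Participants who stopped late in the period.* They have an Early Termination visit and, under Protocol 7.2, may have a further visit at least 28 days after the last dose.

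**4. Stopped at the Week 16 visit.** Assume the Early Termination visit falls 7 days after the Week 16 visit. Distances to target (visit, later record) for visit days 111 to 115:
- T = 118: (7, 0), (6, 1), (5, 2), (4, 3), (3, 4). The later record wins on 4 of 5 days.
- T = 113: (2, 5), (1, 6), (0, 7), (1, 8), (2, 9). The later record wins on 0 of 5 days.

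**5. Stopped late.** Let the last dose be on day L, with visits exactly at L + 7 and L + 28. Both fall in Days 99 to 129 when L is 92 to 101.
- T = 118: the later visit wins when L − 90 ≤ 111 − L, so L ≤ 100, which is 9 of 10 days.
- T = 113: the later visit wins when L − 85 ≤ 106 − L, so L ≤ 95, which is 4 of 10 days.

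The choice changes for L = 96 to 100. Example: L = 100 gives visits on Days 107 and 128. With 118 the distances are 11 and 10, so Day 128 is used. With 113 they are 6 and 15, so Day 107 is used.

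**6. Size.** In group 4, a PASI 90 responder on Day 113 could be scored as a failure, because the selected record follows drug withdrawal. One such participant moves the rate by 1/40 = 2.5 points in the placebo, 200 mg or 400 mg arm, and by 1/20 = 5 points in the 50 mg or 100 mg arm. In group 5 both records follow withdrawal, so both are failures in the primary set and the rate does not move. In the E2 and observed sets, the off-drug score selected as Week 16 can change in both groups.

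**The case against.** **Few participants are affected.** This stands. Most participants have one record in the window. The clearest case needs someone who attends Week 16, is stopped at that visit, takes no Extension drug and returns a week later. Stopping for a laboratory value at the visit itself is unlikely, because Protocol 7.1 requires a confirmatory re-test.

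**The off-drug value is not analysed as recorded in the primary set.** This is true, since SAP 4.4 sets it to failure. It does not remove the problem: selecting that record can still turn a Day 113 responder into a failure. The SAP does not say whether post-withdrawal records are put aside before or after the window selection.

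**The target may have been moved on purpose when the window was widened.** The version history mentions window adjustments but gives no reason for a different Week 16 target. The Week 40 row shows the opposite practice: its window was extended to Day 305 and its target stayed at Day 281.

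**The digit may be an artefact of text conversion.** 113 and 118 differ by one character, so the printed page has to be checked first.

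**A stronger reading that does not hold.** A reader might infer that footnote d lets repeat tests of abnormal laboratory values replace scheduled ones generally and pulls the safety summaries toward normal. The documents do not establish this. SAP 6.8.2 says "Laboratory data will be listed and summarized in accordance with the CaPS reporting standards", and SAP 6.8 sends the safety tables to sponsor standards. Those standards are not reproduced and may give scheduled records priority. Any such effect on by-visit means would in any case be negligible.

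**Conclusion.** Wrong as written, minor. Day 118 conflicts with the protocol's Day 113 and with every other row of the SAP's own table. It is an operative number, because it selects the record for the primary time point.

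The documents do not support reading this as a general bias in the primary result. On the likely reading of footnote b nothing is displaced for participants who continue, and ordinary non-continuers return outside the window. What remains is a handful of participants at most, each worth 2.5 points in an arm of 40 if their primary status changes.

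This rests on four assumptions: the SAP page prints 118; the Week 16 window closes at the first Extension dose; Early Termination and post-dose visits occur at 7 and 28 days; and, for the primary set, the order of programming steps lets the later record through.

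**What to change.** Confirm that the SAP page prints 118, then change the Week 16 target day in Appendix 2.1 to 113. The window limits and footnotes can stay as they are. The cost is one number in the SAP and the matching value in the windowing program. If Week 16 records have already been derived with 118, re-derive them and list any participant whose selected record changes.
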